## **Power Analyses**

All power calculations assume size alpha= 0.05 two-sided tests and requiring power 0.80, and assuming 85% retention (we had 92% retention in our pilot study), so we have 51 subjects per cell. For Hypothesis 1, with a total of 204 patients, we can detect a small effect size of approximately  $f^2 = 0.06$  for the two-way models with an interaction term. For post-hoc direct comparisons involving only the cells of size 51 we have power to detect medium effects of size approximately  $d=0.55$ . For Hypothesis 2, the results of Hedges and Pigott (2004) show that we have power to detect large effects for individual cells. It is well known that tests for moderation can have low power; however, we do expect that our use of optimally combined moderators will enhance our ability to identify key moderators. Finally, for testing potential mediators, previous simulation studies indicate that we have power to detect medium to large effects sizes for the individual cells (MacKinnon, Lockwood, Hoffman, West, & Sheets, 2002).

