**NCT number: NCT03825588**

**IRB approved date: 10-01-21**

# As Safe As Possible (ASAP): A BALANCED, 2X2 DESIGN TO TEST CONJOINT AND UNIQUE EFFICACY OF AN INPATIENT INTERVENTION AND AN EMOTION REGULATION/SAFETY PLANNING APP IN PREVENTING SUICIDE ATTEMPTS POST-DISCHARGE.

## Abstract

**Aims:** One of the highest risk periods for suicidal behavior is in the first 6 months after discharge from psychiatric hospital. In this 2-site study (University of Texas Southwestern Medical Center; UTSW and Western Psychiatric Institute and Clinic; WPIC), we propose to conduct a randomized clinical trial (RCT) in 250 hospitalized suicidal adolescents, examining the single and additive effects of two components of an inpatient unit intervention for suicidal adolescents, As Safe As Possible (ASAP), which focuses on emotion regulation and safety planning, and an emotion regulation/safety plan phone app (BRITE). In a recently completed pilot RCT of 65 suicidal adolescent inpatients, ASAP + BRITE reduced the hazard of suicide attempts over the subsequent 6 months compared to treatment as usual (AU) substantially (adjusted HR=0.22, p=0.03), especially in youth with a previous history of a suicide attempt (HR=0.12, p<0.05). **Methods:** We will randomize 250 hospitalized suicidal adolescents with a history of a suicide attempt or ideation with plan to one of 4 conditions in a 2 by 2 design: (1) ASAP + BRITE + TAU; (2) BRITE + TAU; (3) ASAP + TAU; or (4) TAU alone to determine the single and additive effects of ASAP and BRITE on suicide attempts in the subsequent six months. **Expected Outcomes:** We hypothesize that ASAP and BRITE will each effectively reduce suicide risk post-discharge compared to TAU and that the combination will be superior and more cost effective relative to each individual intervention as well as to TAU.

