In order to identify the most cost-effective component of this intervention, we propose to build on our pilot work by: (1) recruiting a larger, more demographically diverse sample to replicate these findings; (2) disaggregating the effects of ASAP and BRITE through the use of a 2 by 2 design; (3) testing for mediators of treatment outcome; and (4) determining which treatment arm is most cost-effective, and therefore most likely to be acceptable to payers and providers.

Therefore, we aim to randomize 250 adolescents hospitalized, either in a psychiatric unit or a medical unit for a suicide attempt, to one of four treatment arms: (1) ASAP + BRITE + TAU; (2) BRITE + TAU; (3) ASAP + TAU; and (4) TAU alone and assess suicidal ideation and behavior at 1, 3, and 6 months post-intake, in order to:

1. Assess the relative efficacy of ASAP, BRITE and the combination on suicidal ideation, non-suicidal self-injury (NSSI), and suicide attempts, and re-hospitalizations.

H1: Both ASAP and BRITE will be superior to TAU alone, and ASAP + BRITE + TAU will be superior to BRITE or ASAP alone.

2. Examine mediators and moderators of treatment outcome

H2: The effects of ASAP and BRITE will be mediated by increases in reasons for living, decreases in dysfunctional emotional regulation, increases in functional emotional regulation, and decreases in implicit associations with death, and will be moderated by previous history of an attempt, and family engagement in treatment. In addition, the impact of BRITE will be proportional to the frequency of use.

3. To examine the costs and cost efficacy of ASAP and BRITE and the combination.

H3: Both ASAP and BRITE will be more cost-effective than TAU, and the combination of ASAP and BRITE will be more cost-effective than either individual component alone.

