#### Primary aims.

Hypothesis 1. Both ASAP and BRITE will be superior to TAU alone, and ASAP + BRITE + TAU will be superior to BRITE or ASAP alone.

Our main analysis will be the use of two-way ANOVA with an interaction term. We will use the assessments from the instruments listed in Table 1 to study the three main outcomes. For SI severity, we will use a linear model; for NSSI and suicide attempts, we will use a Poisson model; and for the time to attempt, we will use the Cox model. We will include as covariates the following: site, the three covariates we balanced on in our randomization, and any covariates we find in our preliminary analyses to be associated with the outcome; we will consider mixed effects models if they provide a better fit. We do not expect a strong interaction term; if so, our inferences will be based on the main effects. As additional analyses, we will use post-hoc tests for the four main comparisons: the combination vs. each component, and each component vs. TAU.

H2: The effects of ASAP and BRITE will be mediated by increases in reasons for living, decreases in dysfunctional emotional regulation, increases in functional emotional regulation, and decreases in implicit associations with death, and will be moderated by previous history of an attempt, and family engagement in treatment. In addition, the impact of BRITE will be proportional to the frequency of use.

For moderator and mediator analyses, we use the standard approach of Baron and Kenney (1986) and later explicated by Kraemer and colleagues (2002) and Kraemer (2008) for moderators. The search for moderators is typically an exploratory analysis because it involves the testing of interaction terms, for which power is usually limited. Thus, we will use the recent optimal weighted moderator profiles developed by Wallace, Frank, and Kraemer (2013) that combine potential (weaker) moderators. For mediator analyses, we will follow the approach of Preacher and Hayes (2008) for handling multiple mediators. In particular, we will begin by including the candidate mediators listed above in a single model and test their significance using both standard errors using the Gaussian model or the bootstrap if the Gaussian model is not a good fit.

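### The Hypothesis 1 power statement counts 204 retained patients where 85% of 250 is 212, and its 80% power, given only as f² and d, is not shown for suicide attempts

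*Combined protocol and SAP*

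**What the plan says.** Specific Aims sets the enrolment: "we aim to randomize 250 adolescents hospitalized", in a balanced 2×2 design. The Abstract gives the purpose: "to determine the single and additive effects of ASAP and BRITE on suicide attempts in the subsequent six months".

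Power Analyses works at two-sided alpha 0.05 and 80% power, "assuming 85% retention (we had 92% retention in our pilot study), so we have 51 subjects per cell". It continues: "For Hypothesis 1, with a total of 204 patients, we can detect a small effect size of approximately" f² = 0.06 for the two-way model with interaction, and it gives d of about 0.55 for contrasts between single cells. It names no outcome, event rate, rate ratio, hazard ratio or number of events.

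Under Primary aims, Hypothesis 1 is tested with three kinds of model: "For SI severity, we will use a linear model", and "for NSSI and suicide attempts, we will use a Poisson model; and for the time to attempt, we will use the Cox model". On the interaction, the plan says "We do not expect a strong interaction term; if so, our inferences will be based on the main effects".

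Preliminary Data reports pilot attempt rates of 13.3% (combination) and 31.0% (treatment as usual, TAU), and an adjusted hazard ratio (HR) of 0.22 (95% CI 0.05 to 0.85). The pilot had no single-component arm. Power Analyses uses none of these figures.

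**The concern.** There are two separate problems. First, 51 per cell is presented as a consequence of 85% retention, and it is not one for a trial of 250.

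Second, 80% power is attached to Hypothesis 1 as a whole, in measures that belong to a linear model. Hypothesis 1 is also tested on attempts and time to attempt, and attempts are the outcome in the title and Abstract. Power for those outcomes depends on the number of events and the rate or hazard ratio, and the plan states neither.

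The trial is meant to separate ASAP from BRITE and choose a component for dissemination. If power on attempts is never stated, a non-significant main effect could be taken to show that a component does not work, when the trial may have had little chance of detecting it.

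**Working it through.** **1. Retained patients.** Inputs: 250 randomized, four equal cells, 85% retention.
- 250 × 0.85 = 212.5, so 212 in total; 212.5 / 4 = 53.1, so 53 per cell.
- The plan's figure: 51 × 4 = 204; 204 / 250 = 81.6%; 204 / 0.85 = 240. The figure is therefore exactly 85% of 240.

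**2. The plan's effect sizes.**
- Cell contrast, two-sample t-test: d = 0.55 has 78.5% power at 51 per cell and 80.1% at 53. Detectable d is 0.560 and 0.549 respectively.
- Two-way model, non-central F with λ = f² × N: at N = 204, f² = 0.06 has 93.6%, 84.0% and 80.1% power for 1, 3 and 4 numerator df. The plan does not state the df.
- For a 1-df main effect, detectable f² at 80% is 0.0388 at N = 204 and 0.0374 at N = 212 (d = 2√0.0374 = 0.387). The count correction alone changes little; most of the gap from 0.06 comes from using 1 df.

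The stated effect sizes therefore stand, and f² = 0.06 is conservative for the main effects.

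**3. Time to first attempt.** Assumptions: TAU risk 31% at 24 weeks (pilot), no interaction on the hazard scale, effect split equally between components, 53 per cell. Main-effect power by Schoenfeld's formula, with D events, is Φ(½√D × |ln HR| − 1.96).

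*Crude pilot rates*
- Combination HR = ln(0.867) / ln(0.69) = 0.385; component HR = √0.385 = 0.620.
- Single-component risk = 1 − 0.69^0.620 = 20.6%.
- D = 53 × (0.310 + 2 × 0.206 + 0.133) ≈ 45.3.
- Power = Φ(½√45.3 × 0.478 − 1.96) ≈ 36%.
- Events for 80% = 4 × (1.96 + 0.842)² / (ln 0.620)² ≈ 138.

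*Pilot adjusted HR 0.22*
- Component HR = √0.22 = 0.469.
- Applied to the crude TAU risk, cell risks are 31.0%, 16.0%, 16.0% and 7.8%. D ≈ 37.5 and power ≈ 64%.
- Treated as a covariate-adjusted effect at crude event rates, D ≈ 45.3 and power ≈ 72%. This variant is relevant because the plan adjusts: "We will include as covariates the following: site, the three covariates we balanced on in our randomization".
- Events for 80% ≈ 55.

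**4. Sensitivity to the assumptions, 53 per cell.**

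| Scenario | Main-effect power |
|---|---|
| Crude effect, equal split | 36% for each component |
| Crude effect, one-third/two-thirds split | 19% (weaker), 57% (stronger) |
| Crude effect, all in one component (about 47 events) | about 90% for that component, 5% (alpha) for the other |
| Combination HR 0.05 (lower pilot CI limit), equal split | about 97% |
| Combination HR 0.85 (upper pilot CI limit), equal split | about 6% |

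These figures are for time to first attempt. No figure is offered for the Poisson analysis of attempt counts, because the documents give no repeat-attempt rate.

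**The case against.** **The count hardly matters.** This is correct. It is two patients per cell, it errs on the safe side, and the stated d of about 0.55 fits 53 per cell better than 51.

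**The plan never claims 80% power for attempts.** This also stands. A reader might infer such a claim from the unqualified reference to Hypothesis 1, but the section gives only f² and d, and its wording follows the two-way ANOVA. The defect is an omission that invites misreading; it is not a false claim.

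**The low figures depend on an assumed split.** They do. A reader might infer that power on attempts is simply about half of 80%. That holds only at crude pilot rates with an equal split and no interaction. With no single-component arm in the pilot, the documents support no particular split.

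**Dropouts still contribute follow-up to a Cox model.** This is a fair point. With all 250 fully followed, equal-split power rises to about 42% at crude rates and 71–79% at HR 0.22, which only approaches 80% in the most favourable case. The plan itself budgets for 85% retention. Its promise under Removal from the study to follow everyone concerns participants removed from the intervention, not those lost to follow-up.

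**The upper end of 64–72% is generous.** It may be. A simulated Cox analysis with one strong prognostic covariate (assumed log HR 2.0 per SD, a value not found in the documents) gave about 70%, which lies within the range.

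**Conclusion.** The point holds in two parts. The retained sample should read 212 (53 per cell), not 204 (51 per cell); the effect is negligible and the error conservative. The 80% power is supported for linear-model effects and is not shown for attempts or time to attempt.

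Under the equal-split assumptions, about 37–45 first attempts are expected, against 138 (crude rates) or 55 (HR 0.22) needed for 80%. These are scenarios, not limits, because both the split and the pilot HR are very uncertain.

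The documents do not support three stronger readings. The f² = 0.06 figure is not an error. The trial is not shown to be underpowered for attempts under every plausible effect. The match to 240 does not establish that an earlier target was 240: Human Subjects Issues mentions an increased sample size but gives no previous number.

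**What to change.** Reword Power Analyses along these lines:

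> 250 will be randomized; with 85% retention, 212 complete (53 per cell). The f² and d figures apply to ideation severity (linear model): d of about 0.55 for cell contrasts, and f² of about 0.06, which is conservative for 1-df main effects (80% power at about 0.037). 80% power is not claimed for suicide attempts or time to attempt. Assuming a TAU risk of 31%, no interaction and an equal split between components, main-effect power for time to first attempt is about 36% at crude pilot rates and 64–72% at HR 0.22, and it changes greatly with the split. Attempt results will be interpreted from the estimated rate ratio (Poisson) or hazard ratio (Cox) with its 95% confidence interval; a non-significant result alone will not be taken as showing that a component has no effect.

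Enrolment, design and planned models stay as they are. The change adds a commitment on how attempt results are interpreted. It also ties f² and d to ideation severity, which the section does not now say and which the sponsor should confirm. The cost is a less favourable power statement for attempts.

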## **Strengths, Limitations, and Future Plans.**

To our knowledge, this is the first attempt to establish the efficacy of brief interventions to prevent post-discharge suicide attempts in psychiatrically hospitalized suicidal adolescents, the first to establish the

efficacy of safety planning as an intervention, and the first to test the efficacy of a smartphone intervention to reduce suicidal behavior. However, we cannot control the duration and types of treatments that the participants experience while on the inpatient unit and thereafter, although we can document and adjust for the effects of differences to pre- and post-discharge intervention. For example, we can conduct analyses stratified by length of hospitalization as a sensitivity check. In addition, there may be differences with respect to the type, intensity, and duration of outpatient care, although we will gather this information and covary its impact on outcome.

Based on our cost-effectiveness analyses, we will identify the most cost-effective component of our intervention for future dissemination studies, by training inpatient staff on the intervention, and evaluating the effectiveness of this intervention as delivered by inpatient clinicians.

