### Assessments (see Table 1):

Follow-up assessments using independent evaluators blind to treatment condition will be conducted at Weeks 4, 12, and 24. TAU or standard care on the inpatient unit includes diagnosis, safety assessment and stabilization, initiation or adjustment of pharmacotherapy, psychoeducation of patients and families, and disposition. It is standard care for the inpatient units to provide clinical referrals for outpatient treatment and typically a follow-up appointment occurs about 1 week after discharge. We will also directly measure TAU services post hospitalization using a service use assessment instrument (CASA – see measures section).

Demographics, including gender identity and sexual orientation (as per requirements by AFSP research grants) will be collected at baseline. We will compare the four treatment conditions with respect to three main sets of outcomes: (1) efficacy at reducing suicidal ideation, and increasing time to suicidal attempt and (2) moderators and mediators related to suicidal outcomes, (3) cost effectiveness of each intervention alone and combined compared to TAU.

To shorten the diagnostic assessment, dimensional measures of psychopathology will be obtained from the parent, using the Strengths and Difficulties Questionnaire (SDQ; Goodman, 1997) and the corresponding Youth Self Report (YSR) from the participant (Achenbach, 1991) at intake. Diagnostic assessment will include dimensional measures of anxiety (the Screen for Anxiety Related Disorders [SCARED, 5 item scale]) (Birmaher et al., 1999), depression (Patient Health Questionnaire [PHQ-9]) (Johnson, Harris, Spitzer, & Williams, 2002; Richardson et al., 2010), alcohol and drug use (CRAFFT-self report substance use screening tool) (Knight et al., 1999), and sleep disturbance (Pittsburgh Sleep Quality Index [PSQ]; Buysse, Reynolds, Monk, Berman, & Kupfer, 1989). These measures will be obtained at each follow up, since these are often targets of group and individual treatment and because these may be potential moderators of use of the safety plan and of suicidal ideation change.

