### **Statistical analysis.**

We will begin with a preliminary analysis of data, for example to examine missingness patterns, outliers, and consider transformations and dimension reduction methods. Next, we will compare the four groups on demographic and clinical variables to identify any differences between groups. In the regression analyses below, we will include those variables that are related to the main outcomes of the

study. We will also assess site effects and control for them if indicated. Our initial analysis for each hypothesis will be a test of equality of the two or four cells without covariates, using the appropriate (t or F, chi-square, Kaplan-Meier) test for continuous, discrete, and time-to-event data. We will then use appropriate (GLM) regression methods developed by Hedeker and colleagues (Hedeker, Mermelstein, & Demirtas, 2008; Hedeker, Mermelstein, & Demirtas, 2009) for both continuous and discrete data. We will also use the Cox models to study the time to suicidal event, with appropriate modifications if the proportional hazards assumption is in doubt. We will try to ascertain the reason(s) for any missing data in order to decide on how to deal with missingness. We adopt the general approach of Little and Rubin (2002): we will do sensitivity analyses, comparing the results of completers only, last value carried forward, and multiple imputation by chained equations (MICE) and report inferences that are well supported by those analyses. Next, we will address the three secondary aims: our approach to mediation and moderation analysis, and cost-effectiveness analysis are described below. We will also do extensive exploratory analyses to assess the potential effects of other covariates we measure, such as adherence, gender identity, emotion regulation, and sexual orientation. Finally, for all regression analyses, we will use standard regression diagnostics (residual plots, influence measures) to assess the fits of our models, and refine them if indicated by the data.

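### Outpatient care received after randomisation is to be covaried on outcome with no stated role, and the H1 covariate rule is not limited to baseline variables

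*Combined protocol and SAP*

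**What the plan says.** Strengths, Limitations, and Future Plans notes that outpatient care may differ between participants in "type, intensity, and duration of outpatient care, although we will gather this information and covary its impact on outcome". No model, estimand or rank is given for that analysis. The sentence before it does give a role, but to a different analysis: "we can conduct analyses stratified by length of hospitalization as a sensitivity check".

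Under Primary aims, the main H1 analysis is a two-way model. Its covariates are site, the balancing factors and "any covariates we find in our preliminary analyses to be associated with the outcome". On the interaction it says: "We do not expect a strong interaction term; if so, our inferences will be based on the main effects". The Statistical analysis section likewise brings outcome-related variables into the regressions. Neither section limits covariates to those measured at baseline.

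Three statements in Statistical analysis bear on how far this goes:
- Each hypothesis starts with a "test of equality of the two or four cells without covariates".
- The preliminary step is to "compare the four groups on demographic and clinical variables to identify any differences between groups", with no time limit on those variables.
- There will be "extensive exploratory analyses to assess the potential effects of other covariates we measure, such as adherence". Outpatient care is not named there, but the list is open.

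On measurement, the Assessments section says: "We will also directly measure TAU services post hospitalization using a service use assessment instrument". Table 1 schedules that instrument (CASA) at baseline and at Weeks 4, 12 and 24.

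**The concern.** H1 asks whether assignment to ASAP, BRITE or both lowers suicidal outcomes compared with TAU. That is a total effect, and it includes any benefit that comes through better engagement with outpatient treatment. Care received after discharge comes after assignment. If an arm changes it, adjusting for it removes that route. If sicker adolescents also receive more care, the adjustment further mixes severity into the arm comparison. Care recorded up to Week 24 could even follow an attempt and so be partly a result of the outcome.

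The documents make an arm effect on care plausible, though not certain:
- Specific Aims says the ASAP follow-up calls encourage adherence to outpatient treatment. The intervention descriptions say only that the calls assess adherence to follow-up care.
- Up to two calls are described for ASAP and for BRITE alone. None is described for TAU alone.
- The dashboard section allows outpatient clinicians to receive updates on app use. Only the app arms can have this.
- The costing section is built to pick up either a cost offset or extra service use in the active arms.

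Followed literally, the limitations section and the H1 covariate rule could place outpatient care in the main H1 model. If adjusted and unadjusted results then differed, no prior rule would say which one answers H1. A larger sample would not close the gap.

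**Working it through.** **Inputs.** The plan gives no figure on this point. For scale, Power Analyses states a detectable d of about 0.55 with 51 per cell, two-sided 0.05 and power 0.80. This reproduces: power at n = 51 is 0.793 by the normal approximation (52 per cell needed). The path values below are all assumed:
- `a`: arm effect on care, in SD: 0, 0.1, 0.2, 0.5
- `c`: benefit per SD of care: 0 to 0.3
- `b`: correlation of care with unmeasured severity: 0 to 0.5
- `h`: effect of severity on outcome: 0.5

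**Model.** Equal cells, A = ASAP, B = BRITE, within-arm SD of outcome and care both 1:

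`M = a*g(A,B) + b*U + sqrt(1-b^2)*e`

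`Y = -0.3A - 0.3B - c*M + h*U + e'`

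The slope of Y on M given arm is `-c + b*h`. So:

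adjusted contrast = total contrast + (arm contrast in care) x `(c - b*h)`

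A positive shift means the benefit is understated.

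**Case 1: all three active arms raise care equally.** The main effect on care is `[(a-0)+(a-a)]/2 = a/2`, so each 2x2 main effect shifts by `a(c - b*h)/2`.

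| a | b=0, c=0.3 | b=0.5, c=0 |
|---|---|---|
| 0 | 0 | 0 |
| 0.1 | 0.1 x 0.3/2 = +0.015 | -0.1 x 0.25/2 = -0.0125 |
| 0.2 | +0.03 | -0.025 |
| 0.5 | +0.075 | -0.0625 |

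Each component against TAU shifts by twice this: at a = 0.5, +0.15 or -0.125 SD. For scale, 0.15/0.55 is 27% of the plan's detectable pairwise effect. The combination against either component does not shift.

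**Case 2: only the ASAP arms raise care.** The ASAP main effect shifts by `a(c - b*h)`: +0.03 to -0.025 at a = 0.1, and +0.15 to -0.125 at a = 0.5. The BRITE main effect does not shift.

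**Cancellation.** If `c = b*h` (for example b = 0.4, c = 0.2, giving 0.2 = 0.4 x 0.5), there is no shift at any a. What matters is the net association of care with outcome given arm.

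**Simulation of the linear model (n = 1,000,000), ASAP main effect, total then adjusted:**
- Case 1, a = 0.1: -0.316 to -0.301 (b=0, c=0.3); -0.299 to -0.312 (b=0.5, c=0)
- Case 1, a = 0.5: -0.373 to -0.298; -0.301 to -0.364; with b=0.4, c=0.2, -0.348 to -0.348
- Case 2, a = 0.5: -0.443 to -0.295; -0.301 to -0.426
- a = 0: shift under 0.002

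**Event outcomes.** Here the same c and h are read on the log-rate scale. For a main-effect rate ratio of 0.50 in Case 1, 0.50 x exp(0.015) = 0.51 and 0.50 x exp(-0.0125) = 0.49 at a = 0.1. At a = 0.5, 0.50 x exp(0.075) = 0.54 and 0.50 x exp(-0.0625) = 0.47. Poisson simulation at a = 0.5 gave 0.503 to 0.542 and 0.504 to 0.474. A Cox simulation with TAU risk set to the pilot's 31.0% gave hazard ratios of 0.515 to 0.554 and 0.517 to 0.484 at a = 0.5. At a = 0 it gave 0.493 to 0.489 and 0.521 to 0.520, a small change from non-collapsibility alone.

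**Precision given up by not adjusting.** Residual SD falls to `sqrt(1-(c-b*h)^2)`: 0.954 (b=0, c=0.3), 0.968 (b=0.5, c=0) and 1.000 (b=0.4, c=0.2).

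**The case against.** The strongest reply is that the plan does not actually contain the error. The commitment sits in a limitations paragraph, directly after a sentence about a sensitivity check, so a supplementary reading is natural. No section names outpatient care as an H1 covariate. The preliminary comparison of groups may well mean intake variables only. Adherence is already exploratory. The covariate-free tests target the total effect.

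Arm differences in care may also be small. Referrals before discharge, a follow-up appointment typically about a week later, a letter to the outpatient therapist, and recommendations at Weeks 4, 12 and 24 where untreated disorder or non-adherence is found are not confined to the active arms. The pilot summary gives no data on outpatient care by arm.

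Finally, the path values are invented and most shifts are small. With 204 analysed, the standard error of a standardised main effect is about 2/sqrt(204) = 0.14. The Case 1 shifts are then about 0.1 standard errors at a = 0.1 and 0.5 at a = 0.5. Only Case 2 at a = 0.5 reaches about one.

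Most of this stands, and it limits both likelihood and size. It does not remove the gap. The sensitivity label is attached to length of stay, not to outpatient care. Many clinical measures are repeated at every follow-up, so describing the variables as clinical does not restrict them to baseline. The covariate-free test is called the initial analysis, while the covariate-adjusted two-way model is called the main one.

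**Conclusion.** The concern holds, as a conditional risk that is cheap to close. The plan commits to adjusting for a post-randomisation variable without giving that analysis a role, and its H1 covariate rule does not exclude such variables. It does not say that a care-adjusted model will decide H1.

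A care-adjusted contrast departs from the total effect only if an arm changes care and care has a net association with outcome given arm. The size and direction cannot be obtained from the documents. In the assumed settings a main effect moves by 0.0125 to 0.015 SD when all active arms raise care by 0.1 SD, and by up to 0.15 SD when only the ASAP arms raise it by 0.5 SD. The shift can go either way, so the adjustment cannot be called conservative. The case for acting rests on the low cost, not on a demonstrated large bias.

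**What to change.** Two wording changes:
- **Primary aims, H1:** limit the covariates to site, the balancing factors and other variables measured at baseline. Name the balancing factors: this section counts three besides site, while Randomization names age and past attempt versus high ideation, balanced within and across sites.
- **Strengths, Limitations, and Future Plans:** state that any model adjusting for outpatient care is a supplementary or mediation analysis that does not decide H1. Report CASA service use by arm alongside it, so a reader can see whether the arms differed in care.

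The length-of-stay analysis already has its role and needs no change.

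No new data are needed. The costing section already computes service use for each participant in each arm. The one cost is any precision that adjusting for later care might have added, which in the assumed settings is a residual SD smaller by 0% to 4.6%.
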